8.8.2. Post-Treatment Disease Follow-Up

Participants who discontinue study drug for a reason other than disease progression will move into the disease status follow-up period and should be assessed every 9 weeks \pm 7 days by radiologic imaging to monitor disease status. Every effort should be made to collect imaging information regarding disease status until:

- The start of new anticancer therapy: the start of the new treatment should be captured, but the participant should continue to have disease assessments until progressive disease (see below)
- Disease progression (confirmed by an ICR)
- Death
- The end of study

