8.2. Efficacy Assessments

8.2.1. Tumor Imaging

Objective assessment of tumor status is required using appropriate disease-specific techniques, and a central radiologic facility will be used to determine responses, which will be logged into the eCRF. Response Assessment in Neuro-Oncology (RANO) criteria will be used to assess tumor response and progression. Tumor assessment will consist of a brain MRI (alternative modalities [eg, CT scan] should not be substituted for an MRI). Further details can be found in the imaging manual.

The schedule for MRI assessments will be during screening (this will be considered the baseline scan), every 9 weeks (every 3 cycles), and then at EOT (if applicable). Every effort should be undertaken to ensure the scan is done within 7 days of Cycle 1 Day 1, especially in cases of rapid progression, to ensure that a true baseline is captured ([Ellingson et al 2022](#)). Imaging should continue in 9-week intervals regardless of delays in cycle starts. For participants showing a response, a confirmatory scan may be performed a minimum of 4 weeks from the previous scan (per RANO; [Wen et al 2010](#)). For participants showing a progression based on local radiologic review, treatment should not be discontinued until progression of disease has been determined by the ICR unless the principal investigator believes it is in the best interest of the participant to discontinue treatment before receiving confirmation.

For participants who discontinue treatment for reasons other than disease progression, every effort should be made to continue monitoring their disease status by radiographic imaging until the start of new anticancer therapy, documented disease progression by ICR, death, or the end of study, whichever occurs first.

[figure not shown]

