8.8.3. Survival Follow-Up

Once a participant has received the last dose of study drug, has confirmed disease progression, or starts a new anticancer therapy, the participant moves into the survival follow-up period and should be contacted by telephone, email, or visit at least every 8 weeks (\pm 14 days) to assess for survival status until death, withdrawal of consent, or the end of the study, whichever occurs first.

For participants having entered the survival follow-up period of the study, the site will use continuing participant records to supply data on subsequent treatment regimens, tumor assessments (if discontinued treatment for a reason other than progression), and OS in the eCRF. For participants who do not intend to return to the study investigator for their ongoing care, follow-up should be maintained by phone contact, participant records, and public records/databases at intervals of no longer than 8 weeks.

9. ADVERSE EVENTS: DEFINITIONS AND PROCEDURES FOR RECORDING, EVALUATING, FOLLOW-UP, AND REPORTING

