7.3.2. Progression-Free Survival

Progression-free survival is defined as the time from the date of first dose of pemigatinib to the date of the first documented progressive disease or death due to any cause, whichever is first. Progressive disease will be evaluated according to RANO ([Wen et al 2010](#)) and assessed by an ICR. Partial death dates will be handled using the rules described in Section [4.1.4](#). Participants who are alive without progression before the analysis cutoff date will be censored. Censoring for PFS will follow the algorithm outlined in [Table 2](#), which is based on the FDA guidance for industry ([FDA 2015](#), [FDA 2018](#)).

Table 2: Evaluation and Censoring of Progression-Free Survival

Situation	Outcome	Date of Progression or Censoring
No baseline tumor assessments	Censored	Day 1
No valid postbaseline response assessments	Censored	Day 1
Progression documented between scheduled response assessments	Progressed	Date of first overall response of PD
No progression	Censored	Date of last valid radiologic assessment (not NE and not missing)
Study discontinuation for undocumented progression	Censored	Date of last valid radiologic assessment (not NE and not missing)
Study discontinuation for toxicity or other reason	Censored	Date of last valid radiologic assessment (not NE and not missing)
New anticancer treatment including palliative surgery and radiotherapy started	Censored	Date of last valid radiologic assessment (not NE and not missing) on/before starting a new anticancer treatment
Death before first progressive response assessment	Progressed	Date of death
Death between adequate response assessments	Progressed	Date of death
Death or progression after 2 or more missed assessments	Censored	Date of last valid radiologic assessment (not NE and not missing)

This analysis will be based on FAS. Progression-free survival data will be analyzed by the Kaplan-Meier method in Cohorts A and B, respectively. The number of participants who progressed or died and the number of participants censored will be summarized. The Kaplan-Meier curves for PFS will be presented by cohort. The Kaplan-Meier estimate of median PFS will be presented with its 95% CI. The 95% CI will be calculated using the generalization of Brookmeyer and Crowley's method (1982) with log-log transformation (Klein and Moeschberger 1997).

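### Post-treatment imaging is tied to stopping for a reason other than progression, without saying ICR progression, so participants stopped on local progression that ICR reads as non-PD may be censored early in ICR-based PFS and DOR

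*Protocol*

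**What the plan says.** **Endpoints.** Protocol Section 3 and SAP 7.3.2 and 7.3.3 define PFS and DOR on RANO progression assessed by ICR, or death.

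**Stopping treatment.** Protocol 4.1 and 8.2.1 ask that treatment continue after local progression until ICR has ruled, "unless the principal investigator believes it is in the best interest of the participant to discontinue treatment before receiving confirmation". In Protocol 7.1.1 the only progression item among the mandatory reasons to stop is one reported by ICR.

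**Entry to post-treatment imaging.** Protocol 8.8.2: "Participants who discontinue study drug for a reason other than disease progression will move into the disease status follow-up period", with imaging every 9 weeks. Protocol 8.2.1 uses the same condition; for those participants "every effort should be made to continue monitoring their disease status by radiographic imaging until the start of new anticancer therapy", ICR-documented progression, death or end of study. The ICR qualifier appears among the end points of imaging in both sections, but not in the entry condition of either.

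**Survival follow-up.** Protocol 8.8.3: "Once a participant has received the last dose of study drug, has confirmed disease progression, or starts a new anticancer therapy", the participant enters survival follow-up and "should be contacted by telephone, email, or visit at least every 8 weeks". Sites still supply tumor assessments in this period, but only where the stop was for something other than progression, again without naming ICR.

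**Censoring.** SAP Table 2 censors at the last valid radiologic assessment both when there is no progression and when a participant discontinues the study for undocumented progression. Death counts as an event unless 2 or more assessments were missed. New anticancer treatment, including palliative surgery and radiotherapy, leads to censoring at the last valid scan on or before its start. DOR follows the same algorithm.

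**The concern.** The rule that decides who is scanned after stopping and the rule that decides what counts as an event use different notions of progression. A site that stops a participant on local progression can reasonably record progression as the reason. On that coding the participant meets neither the entry condition in 8.2.1 and 8.8.2 nor the tumor-assessment clause in 8.8.3. If ICR then reads the scan as SD or PR, there is no ICR event and no further scan is due.

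The participant is then censored at the point where a clinician judged the tumor to be growing. Kaplan-Meier treats that person as having the same outlook as those still on treatment and stable. If the outlook is in fact worse, ICR PFS and DOR are too high, in a single-arm trial with no control arm carrying the same bias. DOR has few participants to absorb this: at the planned 28% response rate, 0.28 × 82 = 22.96, so about 23 responders in Cohort A, and each one censored early is 1/23, about 4%, of the DOR set. Scans that were not taken cannot be obtained later.

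**Working it through.** The documents give no precision, event count or discordance rate for PFS or DOR, so there is no plan figure to reproduce. (The Cohort A statement of about 80% does reproduce, at 80.1% for 20 or more responders of 82, but it concerns ORR.) The check is a reading of the text, followed by an illustration on assumed inputs.

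**1. Reading the text.** Consider a participant stopped on local progression whose scan ICR reads as non-PD.
- Entry condition in 8.2.1 and 8.8.2: excluded if progression means the local call, included if it means the ICR call. The text does not say.
- Exit condition in 8.8.2 and the list in 7.1.1: both name ICR, which favors inclusion.
- Tumor-assessment clause in 8.8.3: the same ambiguity.
- EOT MRI (Table 3): due only if none was done in the prior month. The scan that prompted the stop will often satisfy that.
- SAP Table 2 with no further scan: censored at the last valid scan, unless death occurs before 2 assessments are missed.

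**2. Simple model, no deaths or new therapy.** Assumed: scans every 9 weeks; ICR PD or death in 50%, 40% and 35% of those at risk in the first three intervals; a share *p* of ICR-non-PD participants stopped on local PD at each scan; 80% of these have an ICR event per later interval.
- Imaging stops, all censored at the stopping scan: 0.50 × 0.60 × 0.65 = 19.5% at 27 weeks, whatever *p* is.
- Imaging continues, *p* = 10%. Interval 2 hazard: 0.90 × 0.40 + 0.10 × 0.80 = 0.44. Of the 0.56 remaining, 0.54 are on treatment and 0.02 already stopped. At scan 2 another 0.054 stop. Interval 3 events: 0.486 × 0.35 + 0.074 × 0.80 = 0.2293, so the hazard is 0.2293 / 0.56 = 0.4095. PFS = 0.50 × 0.56 × 0.5905 = 16.5%.

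**3. Same model with Table 2's rules.** Let a share *n* of those stopped start new therapy at once (censored under either wording), and let a share *d* of the 80% next-interval events be deaths, which count even without imaging. For *p* = 10%, *n* = 50%, *d* = 25%:
- Continue: interval 2 hazard (0.36 + 0.04) / 0.95 = 0.4211; interval 3 hazard (0.1701 + 0.0296) / 0.523 = 0.3818; PFS = 0.50 × 0.5789 × 0.6182 = 17.9%.
- Stop: interval 2 hazard (0.36 + 0.01) / 0.91 = 0.4066; interval 3 hazard (0.1701 + 0.0054) / 0.4914 = 0.3571; PFS = 0.50 × 0.5934 × 0.6429 = 19.1%.

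Upward shift in 27-week PFS, in percentage points:

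| *p* per scan | no deaths counted, no new therapy | *n* = 50%, *d* = 25% | *n* = 75%, *d* = 50% |
|---|---|---|---|
| 5% | 1.5 (18.0 vs 19.5) | 0.6 | 0.2 |
| 10% | 3.0 (16.5 vs 19.5) | 1.2 | 0.4 |
| 20% | 5.7 (13.8 vs 19.5) | 2.4 | 0.9 |

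Only deaths before the next scan date are counted here. Table 2 also counts a death after one missed scan, which would narrow the gaps further. The SAP does not say whether scans that are no longer scheduled count as missed.

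**4. A second model.** Assumed: exponential time to ICR PD with median 9 or 13 weeks; median 20 weeks from PD to death; local PD called one scan before ICR PD in a share *q*; deaths within two scan intervals of the last scan counted; no new therapy; 8,000 simulated participants per row. Exact 27-week PFS with full imaging is 0.5^(27/9) = 12.5% and 0.5^(27/13) = 23.7%, so differences between rows in the continued column are simulation noise.

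| median, *q* | continued | stopped | shift | censored early per 82 |
|---|---|---|---|---|
| 9 weeks, 10% | 12.9% | 14.0% | 1.1 | 2.7 |
| 9 weeks, 20% | 12.3% | 14.5% | 2.2 | 4.8 |
| 9 weeks, 40% | 12.3% | 17.4% | 5.1 | 10.3 |
| 13 weeks, 10% | 24.3% | 25.7% | 1.4 | 2.8 |
| 13 weeks, 20% | 23.6% | 27.0% | 3.4 | 6.4 |
| 13 weeks, 40% | 23.4% | 30.5% | 7.1 | 12.9 |

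Both models agree on direction. Neither sets the size, because every input on discordance is an assumption.

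**The case against.** The strongest reply is that the protocol, read as a whole, keeps these participants in imaging. The default is to wait for ICR before stopping; 7.1.1 lists only ICR progression; 8.8.2 runs until ICR-confirmed progression. How sites code the reason for stopping is not in the documents, and imaging detail is left to a manual that is not included. This stands as far as it goes: early censoring is possible, not certain. But a text that sites can defensibly apply in two ways is itself the defect. Protocol 6.7 also recognizes clinically determined progression as distinct from RANO-determined progression, so coding a local call as progression would not be perverse.

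Three stronger inferences are tempting and not supported.
- *That 8.8.3 moves everyone off imaging at last dose.* Last dose is indeed one of three alternative triggers. But contact may be by telephone, email or visit, tumor assessments continue for those who stopped for other reasons, and Table 3 shows disease and survival follow-up as separate columns. The two periods overlap and need reconciling; 8.8.3 does not itself cancel imaging.
- *That these participants are lost to PFS and DOR.* They stay in the full analysis set, existing scans can still be read by ICR, and a death counts unless 2 or more assessments were missed.
- *That no analysis can help.* The missing scans cannot be recovered, but investigator-assessed response is already planned for ORR, so local progression can be used in a sensitivity analysis.

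Two limits on reach also stand. Extra scans do not change the main analysis once new therapy starts, because Table 2 censors there under either wording. And PFS and DOR are secondary, in a plan whose analyses SAP 3.2 calls exploratory. The primary ORR keeps every participant in the denominator. A response still unconfirmed at the stop might stay unconfirmed under SAP 7.2.1, but that would lower ORR.

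**Conclusion.** The concern holds as an ambiguity in a collection rule that can produce informative censoring of ICR-based PFS and DOR. The direction is upward, provided that participants stopped on local progression are nearer to ICR progression than those who continue. The size is unknown. Under the assumptions shown, the shift in 27-week PFS runs from 0.2 points (few discordant stops, most starting new therapy, many early deaths) to about 7 points (local PD called a scan early in 40%, no new therapy). For DOR the working gives no estimate beyond each early-censored responder being about 4% of the expected Cohort A set. It is worth correcting because the remedy is cheap and must be in place before the scans would be due.

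**What to change.** 1. In Protocol 8.2.1, 8.8.2 and the tumor-assessment clause of 8.8.3, make the condition stopping for any reason other than *ICR-confirmed* disease progression. State that participants stopped on local or clinical progression not confirmed by ICR continue the existing 9-weekly MRI until ICR progression, death or end of study.
2. In 8.8.3, have survival-only contact begin when disease follow-up ends under 8.8.2, in place of last dose as a free-standing trigger.
3. Reconcile imaging after new anticancer therapy: 8.2.1 lists the start of new therapy as an end point, 8.8.1 moves the participant to survival follow-up at that time, and 8.8.2 says disease assessments go on until progression.
4. In the SAP, add a sensitivity analysis that counts local progression without ICR confirmation as a PFS and DOR event at the local date, and state whether scans no longer scheduled count as missed in Table 2.

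Cost: wording in a few protocol sections at the next amendment and a short SAP addition. Some participants have more MRIs on the schedule already in Table 3, and some who are declining may not attend. Sample size and the ORR analysis do not change.

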8.8.3. Survival Follow-Up

Once a participant has received the last dose of study drug, has confirmed disease progression, or starts a new anticancer therapy, the participant moves into the survival follow-up period and should be contacted by telephone, email, or visit at least every 8 weeks (\pm 14 days) to assess for survival status until death, withdrawal of consent, or the end of the study, whichever occurs first.

For participants having entered the survival follow-up period of the study, the site will use continuing participant records to supply data on subsequent treatment regimens, tumor assessments (if discontinued treatment for a reason other than progression), and OS in the eCRF. For participants who do not intend to return to the study investigator for their ongoing care, follow-up should be maintained by phone contact, participant records, and public records/databases at intervals of no longer than 8 weeks.

9. ADVERSE EVENTS: DEFINITIONS AND PROCEDURES FOR RECORDING, EVALUATING, FOLLOW-UP, AND REPORTING

9.1. Definition of Adverse Event

| Adverse Event Definition |
|--|
| 
• An AE is any untoward medical occurrence associated with the use of a drug in humans, whether or not it is considered drug-related.• An AE can therefore be any unfavorable or unintended sign (including an abnormal laboratory finding), symptom, or disease (new or exacerbated) temporally associated with the use of study drug. |
| Additional Guidance for Events Meeting the Adverse Event Definition |
| 
• Any safety assessments (eg, ECG, vital signs measurements), including those that worsen from baseline, considered clinically significant in the medical and scientific judgment of the investigator (ie, not related to progression of underlying disease) are to be reported as an AE.• Abnormal laboratory test results are to be reported as an AE if they are considered clinically meaningful, induce clinical signs or symptoms, require concomitant therapy, or require changes in study drug. Whenever possible, a diagnosis (eg, anemia, thrombocytopenia) should be recorded in the eCRF rather than the abnormal laboratory test result (eg, low hemoglobin, platelet count decreased).• Exacerbation of a chronic or intermittent pre-existing condition/disease, including either an increase in the frequency and/or intensity of the condition, is to be reported as an AE.• New conditions detected or diagnosed after the start of study drug administration are to be reported as an AE.• Signs, symptoms, or the clinical sequelae of a suspected drug-drug interaction are to be reported as an AE.• Signs and/or symptoms from dose administration errors of a study drug (eg, overdose) or a concomitant medication are to be reported as an AE.• "Lack of efficacy," "disease progression," or "failure of expected pharmacological action" will not be reported as an AE or SAE. Such instances will be captured in the efficacy assessments.• A condition that leads to a medical or surgical procedure (eg, endoscopy, appendectomy) will be reported as an AE if it occurs after obtaining informed consent. The procedure should also be documented in the eCRF. If the condition is present before entering the study (prior to signing the ICF), then it should be captured as medical history.• Pre-existing diseases or conditions with expected fluctuations in signs or symptoms should be reported as an AE only if the investigator judges the fluctuation to have worsened more than expected during study participation. |

9.2. Definition of Serious Adverse Event

If an event is not an AE per the definition above, then it cannot be an SAE even if serious conditions are met (eg, hospitalization for signs/symptoms of the disease under study, death due to progression of disease).

| A serious adverse event is defined as any untoward medical occurrence that, at any dose: | |
|---|--|
| a. Results in death | |
| b. Is life-threatening | 
The term "life-threatening" in the definition of "serious" refers to an adverse drug experience that places the participant, in the opinion of the initial reporter, at immediate risk of death from the adverse experience as it occurs. This does not include an adverse drug experience that, had it occurred in a more severe form, might have caused death.
 |
| c. Requires inpatient hospitalization or prolongation of existing hospitalization | 
In general, hospitalization signifies that the participant has been detained (involving at least an overnight stay) at the hospital or emergency ward for observation and/or treatment that would not have been appropriate in the physician's office or outpatient setting. Complications that occur during hospitalization are AEs. If a complication prolongs hospitalization or fulfills any other serious criteria, the event is serious. When in doubt as to whether hospitalization occurred or was necessary, the AE should be considered serious.
 
Hospitalization for elective treatment or planned surgery (eg, stent replacement, hip surgery) is not considered an SAE.
 
Hospitalization for medical interventions in which no unfavorable medical occurrence occurred (ie, elective procedures or routine medical visits) are not considered SAEs.
 |
| d. Results in persistent or significant disability/incapacity | 
The term "disability" means a substantial disruption of a person's ability to conduct normal life functions. This definition is not intended to include experiences of relatively minor medical significance, such as uncomplicated headache, nausea, vomiting, diarrhea, influenza, and accidental trauma (eg, sprained ankle), that may interfere with or prevent everyday life functions but do not constitute a substantial disruption. |
| e. Is a congenital anomaly/birth defect | |
| f. Is an important medical event | 
An important medical event is an event that may not result in death, be immediately life-threatening, or require hospitalization but may be considered serious when, based on appropriate medical judgment, the event may jeopardize the participant and may require medical or surgical intervention to prevent one of the outcomes listed in the above definition. Examples of such events include new invasive or malignant cancers (excluding the disease[s] under study), intensive treatment in an emergency department or at home for allergic bronchospasm, blood dyscrasias, or convulsions that do not result in hospitalization, or development of drug dependency or drug abuse. Secondary malignancies should always be considered SAEs.
 
For Japan, an event that may lead to disability is also considered an important medical event. It includes a case that is exposed to a risk of dysfunction to an extent that interferes with daily life when the adverse drug reaction occurs. It does not include an adverse drug reaction that, had the reaction been more severe, may have caused disability.
 |

9.3. Recording and Follow-Up of Adverse Events and/or Serious Adverse Events

Adverse Event and Serious Adverse Event Recording

- An AE/SAE that begins or worsens after informed consent is signed should be recorded on the Adverse Event Form in the eCRF. AEs/SAEs should be reported for enrolled participants, but only SAEs need to be reported for screen failure participants. For enrolled participants, conditions that were present at the time informed consent was given should be recorded on the Medical History eCRF. For detailed information refer to the eCRF guidelines.
- When an AE/SAE occurs, it is the responsibility of the investigator to review all documentation (eg, hospital progress notes, laboratory reports, and diagnostic reports) related to the event.
- The investigator (or delegate) will then record all relevant AE/SAE information in the eCRF.
- It is **not** acceptable for the investigator to send photocopies of the participant's medical records in lieu of completing the Adverse Event Form in the eCRF.
- There may be rare instances when copies of medical records for certain cases are requested. In this case, all participant identifiers, with the exception of the participant number, will be redacted by the site staff on the copies of the medical records before submission. These records can be submitted to Incyte Pharmacovigilance by email/fax per the contact information listed in the Study Reference Manual or as per SAE completing guidelines.
- The investigator will attempt to establish a diagnosis of the event based on signs, symptoms, and/or other clinical information. Whenever possible, the diagnosis (not the individual signs/symptoms) will be documented as the AE/SAE. When a clear diagnosis cannot be identified, each sign or symptom should be reported as a separate AE/SAE.

To the extent possible, each AE/SAE should be evaluated to determine the following:

- The severity grade (CTCAE v5.0 Grade 1 to 5). See below for further instructions on the assessment of intensity.
- Whether there is at least a reasonable possibility that the AE is related to the study drug: suspected (yes) or not suspected (no). See below for further instructions on the assessment of causality.
- The start and end dates, unless unresolved at the final safety follow-up visit.
- The action taken with regard to study drug as a result of the AE/SAE(s).
- The event outcome (eg, not recovered/not resolved, recovered/resolved, recovering/resolving, recovered/resolved with sequelae, fatal, unknown).
- The seriousness, as per the SAE definition provided in Section 9.2.
- The action taken with regard to the event. Note: If an AE is treated with a concomitant medication or nondrug therapy, this action should be recorded on the Adverse Event Form, and the treatment should be specified on the appropriate eCRF (eg, Prior/Concomitant Medications, Procedures and Non-Drug Therapy).

Assessment of Intensity

The severity of AEs will be assessed using CTCAE v5.0 Grades 1 through 5. If an event is not classified by CTCAE, the severity of the AE will be graded according to the scale below to estimate the grade of severity.

The investigator will make an assessment of intensity for each AE and SAE reported during the study and assign it to 1 of the following categories:

- **Grade 1:** Mild; asymptomatic or mild symptoms; clinical or diagnostic observations only; treatment not indicated.
- **Grade 2:** Moderate; minimal, local, or noninvasive treatment indicated; limiting age-appropriate activities of daily living.
- **Grade 3:** Severe or medically significant but not immediately life-threatening; hospitalization or prolongation of hospitalization indicated; disabling; limiting self-care activities of daily living.
- **Grade 4:** Life-threatening consequences; urgent treatment indicated.
- **Grade 5:** Fatal.

Assessment of Causality

- The investigator is obligated to assess the relationship between study drug and each occurrence of each AE/SAE.
- A "reasonable possibility" of a relationship conveys that there are medical facts, evidence, and/or arguments to suggest a causal relationship, rather than that a relationship cannot be ruled out.
- The investigator will use clinical judgment to determine the possibility of a relationship.
- The investigator will also consult the RSI in the IB in making his/her assessment.
- Alternative causes, such as underlying or concurrent disease(s), concomitant therapy, and other risk factors, as well as the temporal relationship of the event to study drug administration, will be considered and investigated.
- For each AE/SAE, the investigator **must** document in the medical notes that he/she has reviewed the AE/SAE and has provided an assessment of causality.
- With regard to assessing causality of SAEs:
 - There may be situations in which an SAE has occurred and the investigator has minimal information to include in the initial report. However, the causality assessment is one of the criteria used when determining regulatory reporting requirements. **Therefore, it is very important that the investigator always make an assessment of causality based on the available information for every event before the initial transmission of the SAE.**
 - The investigator may change his/her opinion of causality in light of follow-up information and submit the updated causality assessment.

Follow-Up of Adverse Events and Serious Adverse Events

- The investigator is obligated to perform or arrange for the conduct of supplemental measurements and/or evaluations as medically indicated or as requested by the sponsor to elucidate the nature and/or causality of the AE or SAE as fully as possible. This may include additional laboratory tests or investigations, histopathological examinations, or consultation with other health care professionals.
- Once an AE is detected, it should be followed in the AE eCRFs until it has resolved or until it is judged to be permanent; assessment should be made at each visit (or more frequently if necessary) of any changes in severity, the suspected relationship to the study drug, the interventions required to treat the event, and the outcome.
- When the severity of an AE changes over time for a reporting period (eg, between visits), each change in severity will be reported as a separate AE.
- If a participant dies during participation in the study or during a recognized follow-up period, the investigator will provide the sponsor with a copy of any postmortem findings, including histopathology.
- Updated SAE information will be recorded in the originally completed eCRF and reported to Incyte Pharmacovigilance (in the SAE EDC CRF) until resolution, stabilization, the event is otherwise explained, or the participant is lost to follow-up.
- Any updated SAE data (including SAEs being downgraded to nonserious) will be submitted to the sponsor (or designee) within 24 hours of receipt of the information.

